9.2 Recording adverse events

All adverse events will be recorded in the participant's research consultant navigator in the electronic health record system, EPIC and in the CRF. All adverse events will be recorded with clinical symptoms and accompanied with a simple, brief description of the event, including dates as appropriate from consent until 10 weeks after they finish IMP (phone call at 58 weeks). From the 58 week phone call and the 96 week visit only AEs related to IMP or other trial intervention need to be recorded in the CRF.

9.3 Assessments of Adverse Events

Each adverse event will be assessed for severity, causality and seriousness as described below.

9.3.1 *Severity*

The severity of all AEs and/or ARs (serious and non-serious) in this trial should be graded using the study specific toxicity grading system and the National Institutes of Health Common Terminology Criteria for

Short title: Exenatide once-weekly as a treatment for Multiple System Atrophy Sponsor code: 125591

Adverse Events (CTCAE) version 5.0. SUSARs will be coded via MedDRA for the purpose of expedited reporting to MHRA/REC.

Where the specific event term is not listed in CTCAE please refer to the below table:

Grade	Definition
Grade 1	Mild; asymptomatic or mild symptoms; clinical or diagnostic observations only; intervention not indicated.
Grade 2	Moderate; minimal, local or noninvasive intervention indicated; limiting age-appropriate instrumental ADL*.
Grade 3	Severe or medically significant but not immediately life-threatening; hospitalization or prolongation of hospitalization indicated; disabling; limiting self-care ADL**.
Grade 4	Life-threatening consequences; urgent intervention indicated.
Grade 5	Death related to AE.

*Instrumental ADL refer to preparing meals, shopping for groceries or clothes, using the telephone, managing money, etc.

**Self-care ADL refer to bathing, dressing and undressing, feeding self, using the toilet, taking medications, and not bedridden.

9.3.2 *Causality*

The assessment of relationship of adverse events to the administration of IMP is a clinical decision based on all available information at the time of the completion of the case report form.

The following categories will be used to define the causality of the adverse event:

Category	Definition
Related:	A causal relationship between an IMP/investigational treatment and an adverse event is at least a reasonable possibility , i.e., the relationship cannot be ruled out.
Not related	There is no reasonable possibility of a causal relationship between an IMP/investigational treatment and an adverse event.

9.3.3 *Expectedness*

Short title: Exenatide once-weekly as a treatment for Multiple System Atrophy Sponsor code: 125591

Category	Definition
Expected	An adverse event which is consistent with the information about the IMP listed in the current approved Reference Safety Information (RSI) for the trial.
Unexpected	An adverse event which is not consistent with the information about the IMP listed in current approved Reference Safety Information (RSI) for the trial.

The RSI to be used to assess expectedness against the IMP is:

SmPC for Bydureon (exenatide) 2 mg for prolonged-release suspension for injection in pre-filled pen (BCise) (AstraZeneca UK Limited).

The following events listed below describe expected procedural/disease related AEs: The most frequent adverse reactions were mainly gastrointestinal related (nausea which was the most frequent reaction and associated with the initiation of treatment and decreased over time, and diarrhoea). In addition, injection site reactions (pruritus, nodules, erythema), hypoglycaemia (with a sulphonylurea), and headache occurred. Most adverse reactions associated with prolonged-release exenatide were mild to moderate in intensity.

9.3.4 *Seriousness*

All events are assessed for seriousness as defined for an SAE in section 9.1. Specific adverse events that require expedited reporting as SAEs are detailed in section 9.3.5.

9.3.5 *Other Notifiable Adverse Events*

Suspicion of chronic pancreatitis based on a rise in serum amylase greater than 50% above both baseline level AND the laboratory reference range will be notified in an expedited manner in the same way as an SAE.

Overdose and potential drug induced liver injury (DILI) events must be handled as SAEs (see section 9.8).

All safety events as described above will be treated as SAEs and reported in line with the procedures set-out in section 9.4 apart from regulatory reporting.

9.4 Procedures for recording and reporting Serious Adverse Events

All serious adverse events (SAEs/SARs/SUSARs) will be recorded in the medical records and the CRF, and the sponsor's SAE Recording Log. The SAE Recording Log of SAEs will be reported to the sponsor at least once or twice per year.

All SAEs will be recorded from baseline visit until 10 weeks after completion of IMP (phone call at 58 weeks). From the 58 week phone call and the 96 week visit only SAEs related to IMP or other trial intervention need to be recorded in the CRF.

All SAEs must be recorded on a Serious Adverse Event (SAE) Reporting Form. The CI/PI or designated individual will complete the sponsor's SAE Reporting Form and the form will be

Short title: Exenatide once-weekly as a treatment for Multiple System Atrophy Sponsor code: 125591

emailed to the Sponsor [contact] and within 24 h of his / her becoming aware of the event. The Chief or Principal Investigator will respond to any SAE queries raised by the sponsor as soon as possible.

Completed SAE forms must be sent within 24 hours of becoming aware of the event to the Sponsor
Email forms to [contact]

[figure not shown]
Reporting to the sponsor will be completed as per the sponsor's SOP and using the UCL SAE Reporting Form (INV/S05) as amended for the trial.

SAEs will be reported to the sponsor until the end of the trial. SAR and SUSAR will need to be reported to the Sponsor irrespective of how long after IMP administration the reaction has occurred.

Participants must be followed up until clinical recovery is complete and laboratory results have returned to normal or baseline values, or until the event has stabilised. Follow-up should continue after completion of protocol treatment and/or trial follow-up if necessary.

Follow-up SAE forms (clearly marked as follow-up) should be completed and emailed to the JRO as further information becomes available.

Flow Chart for SAE reporting

9.5 Reporting SUSARs

The sponsor will notify the main REC and MHRA of all SUSARs. SUSARs that are fatal or life-threatening must be notified to the MHRA and REC within 7 days after the sponsor has learned of them. Other SUSARs must be reported to the REC and MHRA within 15 days after the sponsor has learned of them.

9.6 Development Safety Update Reports

The sponsor will provide the main REC and the MHRA with Development Safety Update Reports (DSUR) which will be written in conjunction with the trial team and the Sponsor's office. The report will be submitted within 60 days of the Developmental International Birth Date (DIBD) of the trial each year until the trial is declared ended.

9.7 Pregnancy

There is no safety data to inform on the use of Exenatide during pregnancy. Male participants and female participant of child-bearing potential will be advised to use an effective form of contraception whilst they are on the study. If it is subsequently discovered that a study subject is pregnant or may have been pregnant at the time of IMP exposure, including duration of at least 10 weeks after product administration, the IMP will be permanently discontinued in an appropriate manner.

Protocol-required procedures for study discontinuation and follow-up must be performed on the subject unless contraindicated by pregnancy. Other appropriate pregnancy follow-up procedures should be considered if indicated. Trial follow up assessments will continue as per protocol. The patient's General Practitioner will be informed of the potential unknown risk that may have followed Exenatide exposure during pregnancy.

Pregnancy is not a SAE and should be reported through a Pregnancy Reporting Form. The pregnancy outcome may or may not be considered a SAE.

If a female participant or the female partner of a male participant becomes pregnant at any point during the trial, a completed trial specific Pregnancy Reporting Form will be preferably emailed to the Sponsor **[contact]**, within 24 hours of his / her becoming aware of the event in line with the Sponsors SOP (JRO/INV/S05). The Chief or Principal Investigator will respond to any queries raised by the sponsor as soon as possible.

Completed Pregnancy Reporting Forms must be sent within **24 hours** of becoming aware of the event to the Sponsor
Email forms to [contact]

The Sponsor must be kept informed of any new developments involving the pregnancy through the completion of a follow-up Pregnancy Reporting Form. Any pregnancy that occurs in a female trial subject during a clinical trial should be followed to termination or to term.

Short title: Exenatide once-weekly as a treatment for Multiple System Atrophy Sponsor code: 125591

Consent to report information regarding the pregnancy must be obtained from the pregnant participant or pregnant partner. A trial-specific pregnancy monitoring information sheet and informed consent form for trial participants or pregnant partners must be used for this purpose.

With consent additional information regarding the pregnancy will be collected and reported to the Sponsor, the Sponsor will advise on the length of follow up of the pregnancy/ child on a case by case basis.

9.8 Overdose

An overdose is defined as the accidental or intentional administration of any dose of a product that is considered both excessive and medically important and it must always be reported as a SAE. Overdoses will be fully described in the SAE report form and recorded on the deviation log. Overdoses can be observed from administration diaries, participant and carers comments.

9.9 Reporting Urgent Safety Measures and other safety events

If any urgent safety measures are taken the CI/ PI shall immediately and in any event no later than 3 days from the date the measures are taken, give written notice to the MHRA, the relevant REC and Sponsor of the measures taken and the circumstances giving rise to those measures.

9.10 Notification of Serious Breaches to GCP and/or the protocol (SPON/S15)

A “serious breach” is a breach which is likely to effect to a significant degree –

- (a) the safety or physical or mental integrity of the participants of the trial; or
- (b) the scientific value of the trial.

The sponsor of a clinical trial shall notify the licensing authority in writing of any serious breach of –

(a) the conditions and principles of GCP in connection with that trial; or (b) the protocol relating to that trial, as amended from time to time, within 7 days of becoming aware of that breach.

The sponsor will be notified immediately of any case where the above definition applies during the trial conduct phase. The sponsor's SOP on the 'Notification of violations, urgent safety measures and serious breaches' will be followed.

10 Data management and quality assurance

10.1 Confidentiality

All data will be handled in accordance with the UK Data Protection Act 2018.

The Case Report Forms (CRFs) will not bear the subject's name or other personal identifiable data

The participant's initials, date of birth and trial identification number, will be used for identification and this will be clearly explained to the patient in the Patient information sheet. Patient consent for this will be sought.

10.2 Data collection tools and source document identification

The majority of study data will be collected from the sites on an electronic CRF and into the participant's electronic health records system, EPIC.

Source data are contained in source documents and must be accurately transcribed on to the electronic CRF. Examples of source documents are electronic medical records which include laboratory and other clinical reports etc.

A source document list will be implemented prior to the start of the trial to identify:

which data is to be recorded directly onto the CRF;

which data is not to be recorded in the CRF but only recorded in source documents, e.g., participant questionnaires and diary cards.

It is the responsibility of the investigator to ensure the accuracy of all data entered in the eCRF. The delegation log will identify all those personnel with responsibilities for data collection and handling, including those who have access to the trial database. The electronic CRF will be purpose built and tested for completeness before activation of the site.

10.3 Completing Case Report Forms

All CRFs must be completed and signed by staff that are listed on the site staff delegation log and authorised by the CI to perform this duty. The CI is responsible for the accuracy of all data reported in the CRF. Source data verification of a CRF page should be completed and all data queries answered prior to entry into the database where possible.

10.4 Data handling and analysis

A trial specific data management SOP will be in place for the trial. This will contain details of the software to be used for the database, the process of database design, coding, data entry, data quality checks, data queries, data security, database lock and data transfer. Data queries will be resolved by the trial manager through direct discussion with the trial team. A custom designed database will be created to store all trial data. The database will only be available to specified users who will require a username and password for access.

Where data are transferred electronically this will be in accordance with the UK Data Protection Act 2018 as well as UCL Information Security Policy and Trust Information Governance Policy. There will be a documented record of data transfer and measures in place for the recovery of original information after transfer.

11 Statistical Considerations

11.1 Outcomes

11.1.1 Primary outcomes

The primary outcome will be the difference in total Unified Multiple System Atrophy Rating Scale (UMSARS) score (Parts I and II) at 48 week comparing Exenatide to best medically treated patients. The analysis will use ANCOVA to allow adjustment for baseline severity and MSA sub-type.

11.1.2 Secondary & Exploratory outcomes

Key secondary outcomes would include proportion of patients with loss of independent ambulation by the end of week 48 and 96, defined by a score of 4 or more in UMSARS-I item 7 (walking); difference at Week 48 and 96 in the MSA-QoL scale; difference at Week 48 and 96 in UMSARS Part I, II, III and IV; difference in anti-parkinsonian or anti-orthostatic hypotension drugs; number of falls; and the proportion of patients reaching a score of 3 or more on UMSARS-I items 1 (speech), 2 (swallowing), and 8 (falling); difference in Week 48 and 96 in clinical global impression (CGI); difference at Week 48 and 96 in MoCA scores.

11.2 Sample size and recruitment

11.2.1 Sample size calculation

The recent rasagiline for MSA (MSA-Ras) trial evaluated rasagiline versus placebo using the UMSARS total (Parts I and II) as the primary efficacy measure after 48 weeks treatment. Patients in the placebo group declined by mean 7.8 points (SD 10.4 – Werner et al. 2015).

Therefore, on the basis of this previously collected data and with a two-sided 5% significance level, we estimated that a sample size of 40 patients (20 per group) would be required to detect a difference of 5 total UMSARS points between the two groups, assuming a correlation between baseline and final disease severity of 0.85. These calculations were based on a common SD of 10.4, 80% power and an overall type 1 error rate of 5%. A 5 point difference between groups would be a clinically important effect size. Based on a 20% dropout rate as reported from previous trials, the sample size would be 50 (25 per arm).

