5.1 Overall design

This is a non-commercial, open label trial of a licensed drug designed to primarily provide preliminary efficacy and safety data for the use of Exenatide in MSA. This will be a simple parallel group design and include a 48-week exposure period. Detailed evaluations will take place at Screening, Baseline, 12, 24, 36, 48 and 96 weeks.

Patients will be randomly allocated into 2 groups to receive either:

- Exenatide extended release 2mg subcutaneous injection once weekly for 48 weeks together with standard treatment options, n~25,
or
- Standard treatment options, n~25

[figure not shown]
The control arm will attend all the same visits as the Exenatide group. Separate randomisation lists will be generated for patients with MSA-P or MSA-C.

The control group of patients are very important in view of the continued neurodegenerative process of MSA that leads to a mean 7.8 point decline in UMSARS scores per year (Poewe et al. 2015).

All participants will be invited for face to face visits at all timepoints. If a participant is unable or unwilling to attend any of the follow up assessments (12,24,36,48,96 weeks), they may be offered the option of a home visit by 1 or more members of the trial clinical team if staffing levels permit.

This trial will also assess the safety and tolerability of Exenatide when administered to patients with MSA. Encouraging results will be used as a basis for application for funding for a larger double blind placebo controlled RCT and will be used to inform upon sample size calculations for such a trial. This drug already has a license for the treatment of patients with Type II Diabetes and there is extensive safety data from phase 3 trials of its use in this patient group.

.

6 Investigational Medicinal Products and Non-Investigational Medicinal Products

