#### 4.3 Sample size

The recent rasagiline for MSA (MSA-Ras) trial evaluated rasagiline versus placebo using the UMSARS total (Parts I and II) as the primary efficacy measure after 48 weeks treatment. Patients in the placebo group declined by mean 7.8 points (SD 10.4 – Werner et al. 2015).

Therefore, on the basis of this previously collected data and with a two-sided 5% significance level, we estimated that a sample size of 40 patients (20 per group) would be required to detect a difference of 5 total UMSARS points between the two groups, assuming a correlation between baseline and final disease severity of 0.85. These calculations were based on a common SD of 10.4, 80% power and an

overall type 1 error rate of 5%. A 5-point difference between groups would be a clinically important effect size. Based on a 20% dropout rate as reported from previous trials, the sample size would be 50 (25 per arm).

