## 7.2 Primary outcome Analysis

The primary outcome is the total Unified Multiple System Atrophy Rating Scale (UMSARS) score (Parts I and II) at 48 weeks. The primary analysis will compare exenatide patients to be best medically treated patients using a two-level mixed model that includes the total UMSARS scores from four time-points (12 weeks, 24 weeks, 36 weeks and 48 weeks) with interaction terms between the intervention and time-point indicator variables to enable estimation of the effect of intervention at 48 weeks. This model will also adjust for baseline UMSARS score and MSA subtype using fixed effects.

In detail, the primary analysis will involve fitting the model

$$UMSARS_{ij} = \beta_0 + \beta_1 TRT_i + \beta_2 j TIME_j + \beta_3 j TRT_i \times TIME_j + \beta_4 UMSARS0_i + \beta_5 MSA_i + u_i + \epsilon_{ij}$$

to patients  $i = 1, \dots, 48$  and time-points  $j = 12, 24, 38$  and 48 weeks, where  $UMSARS_{ij}$  and  $UMSARS0_i$  are the UMSARS total scores for patient  $i$  at time-point  $j$  and baseline respectively,  $TRT_i$  is the intervention group indicator (0=standard; 1=Exenatide),  $TIME_j$  are time-point indicators,  $MSA_i$  is a MSA subtype indicator, and  $u_i \sim N(0, \sigma_u^2)$  and  $\epsilon_{ij} \sim N(0, \sigma^2)$  are error terms. All modelling assumptions will be checked.

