## 7.5 Sensitivity analyses

Several sensitivity analyses will be performed for the primary outcome. These are:

- The effect of the intervention will be assessed using a single-level linear regression model, adjusted for MSA subtype and baseline severity.
- If adherence is deemed to be an issue, per-protocol and complier average causal effect (CACE) analyses will be performed.

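### The SD of 10.4 is described as the SD of a 48-week decline but used as the SD of the score; on the first reading, power for 5 points is about 34%, not 80%

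*Protocol*

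**What the plan says.** Protocol 11.2.1 bases the sample size on the placebo arm of an earlier rasagiline trial in MSA: "Patients in the placebo group declined by mean 7.8 points (SD 10.4". Protocol 5.1 uses the same 7.8 in the same sense, saying that the disease "leads to a mean 7.8 point decline in UMSARS scores per year". The second paragraph of 11.2.1 then gives the calculation: 20 per group to detect 5 UMSARS points, "with a two-sided 5% significance level", "assuming a correlation between baseline and final disease severity of 0.85. These calculations were based on a common SD of 10.4, 80% power". Allowing for 20% dropout, this becomes 50 patients. SAP 4.3 repeats both statements, including "These calculations were based on a common SD of 10.4, 80% power".

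Neither document gives a separate SD for the baseline or week-48 score, or a source for the correlation of 0.85.

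The protocol's primary analysis is ANCOVA at week 48. SAP 7.2 replaces it with a "two-level mixed model that includes the total UMSARS scores from four time-points" and keeps a "single-level linear regression model, adjusted for MSA subtype and baseline severity" as a sensitivity analysis (SAP 7.5). The sample-size text was not changed to match.

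**The concern.** An SD quoted beside a mean decline is, on its plain reading, the SD of the decline. The calculation instead treats 10.4 as the between-patient SD of the score and then shrinks it for the baseline correlation. A change score has already had the baseline subtracted. If 10.4 is a change SD, applying the full reduction for a correlation of 0.85 credits the baseline twice.

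This calculation is the only justification given for 50 patients. If the plain reading is right, the trial is much less precise than both documents say, and a null result would say little about a 5-point effect that they call clinically important. Protocol 5.1 also says the results will inform the sample size of a larger placebo-controlled trial, so a misread SD could be carried forward.

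**Working it through.** **Inputs** (Protocol 11.2.1, repeated in SAP 4.3): difference 5 points; two-sided 5%; 80% power; SD 10.4; baseline-to-final correlation r = 0.85; 20 per group evaluable; 20% dropout. Powers below use the noncentral t distribution. Equal SDs at the two visits are assumed unless stated; the documents give no visit SDs.

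**1. The plan's own figure, with 10.4 as the score SD**

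- Residual SD = 10.4 × √(1 − 0.85²) = 5.48.
- Power for 5 points at 20 per arm = 80%. The smallest n reaching 80% is 20 per group.
- 95% CI half-width at 20 per arm = 3.5 points.
- Dropout: 40 / 0.8 = 50.

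The arithmetic reproduces. Without the baseline reduction, SD 10.4 would need 68 per group (normal approximation). A change-score analysis gives 21 per group, but it too takes 10.4 as the score SD.

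**2. Can all the inputs hold together?**

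- With equal visit SDs, change SD = score SD × √(2(1 − r)) = 10.4 × √0.30 = 5.70.
- For week-48/baseline SD ratios of 0.8 to 1.4, the implied change SD is 5.5 to 6.9 if 10.4 is the week-48 SD, and 5.5 to 7.9 if it is the baseline SD.

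None of these reaches 10.4, so at least one input or its description is wrong.

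**3. If 10.4 is the change SD (r = 0.85)**

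- Score SD = 10.4 / √0.30 = 18.99.
- ANCOVA residual SD = 18.99 × √(1 − 0.85²) = 10.0.
- SE at 20 per arm = 10.0 × √(2/20) = 3.16.

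| Evaluable per arm | Power, 5 points | Power, 7.8 points | 95% CI half-width | Difference detectable with 80% power |
|---|---|---|---|---|
| 20 | 34% | 67% | 6.4 | 9.1 |
| 24 | 40% | 75% | 5.8 | 8.3 |
| 25 | 41% | 77% | 5.7 | 8.1 |

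The row for 24 is there because the SAP 7.2 model indexes 48 patients; an equal split is assumed. A 7.8-point difference would be complete arrest of the quoted decline. An observed 5-point benefit at 20 per arm would carry a 95% CI of about −1.4 to 11.4, against 1.5 to 8.5 under the stated inputs. Reaching 80% power for 5 points would take 64 per arm.

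**4. Sensitivity to the unstated quantities** (change SD 10.4, 20 per arm)

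- r varied, equal SDs: r = 0.5 gives 40%; r = 0.95 gives 32%.
- SD ratio varied, r = 0.85: 0.8 gives 46%; 0.9 gives 38%; 1.2 gives 32%; 1.4 gives 33%.
- Both varied (r from 0.5 to 0.95, ratio from 0.8 to 1.4): power 32% to 54%, half-width 4.8 to 6.7 points.
- At r = 0.85, 80% power needs a week-48 SD of only about 0.59 of the baseline SD.
- Baseline ignored, change analysed directly with SD 10.4: 32%.

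**5. Does the SAP mixed model recover the power?**

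The model was simulated on 20,000 complete-data trials at 20 per arm: random intercept, four visits, treatment-by-time terms, baseline covariate, subtype omitted. Assumptions were linear progression, change SD 10.4, r = 0.85, equal SDs at baseline and week 48, and visit-level noise SD of 2 to 7. The true SE of the week-48 effect was 3.19 to 3.21, against 3.16 for ANCOVA. At a true 5% level that is power of about 35%. The model's own SE was smaller (2.3 to 3.1) and it rejected in 37% to 57% of trials. It also rejected in 6% to 17% of trials with no effect, so the excess is not real power.

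**The case against.** The strongest reply is that the consequence depends on a source that cannot be seen here. The documents never call 10.4 an SD of change in so many words. If it is a cross-sectional SD, the 80% is right and one sentence is badly worded. That stands, and it is why the 34% is conditional. It does not rescue the text, because on that reading the sentence in both documents is wrong.

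A second reply is that this is a pilot whose aim is estimation, and whose reported intervals will come from the observed variance. That softens the practical effect. But both documents claim 80% power outright, and estimation depends on precision, which changes by nearly a factor of two between the readings (6.4 against 3.5 points).

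A third reply is that the correlation may be the faulty input. This is fair: no source is given for 0.85, and 10.4 can be both the score SD and the change SD if r = 0.5, since √(2 × 0.5) = 1. Power is then 40%, so this route does not restore 80% either. It is, however, a reason to check the correlation along with the SD. Holding r at 0.85 with a change SD of 10.4 implies a score SD of about 19, and whether that is plausible under the early-stage entry limits in Protocol 7.3 cannot be judged from the documents.

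Finally, the arithmetic in the plan is sound. The fault lies in what the SD is taken to mean.

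**Conclusion.** The concern holds. As written, Protocol 11.2.1 and SAP 4.3 use 10.4 in two incompatible senses, and that conclusion needs no outside source. If the description is right and 10.4 is the SD of the 48-week change, power for 5 points is about 34% at 40 evaluable patients and 41% if all 50 are evaluable. The first figure rests on r = 0.85, equal visit SDs and a single-time-point ANCOVA; relaxing the first two moves it between 32% and 54%. If 10.4 is the score SD, the 80% claim stands and the description is wrong. The documents cannot show which branch applies, but both sections need correcting in either case.

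**What to change.** Keep n = 50. Check in the cited source which SD 10.4 is, and state where the correlation of 0.85 comes from. Then correct Protocol 11.2.1 and SAP 4.3 together:

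- **If 10.4 is the change SD:** replace the claim of 80% power for 5 points with the recomputed power and expected CI half-width. With the present correlation these are about 34% and 6.4 points at 40 evaluable patients. State the equal-SD assumption and the range, and label the figures as single-time-point ANCOVA approximations to the SAP 7.2 model. It would help to add that a non-significant result will not be read as evidence of no effect.
- **If 10.4 is the cross-sectional score SD:** keep the power figure and correct the sentence that attaches 10.4 to the decline.

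The cost is one check of the source and new wording in two sections, with no extra patients and no change to the endpoint or analysis. On the first branch, the stated power becomes less favourable.
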